7.2.7 Medical Histories

Medical history will be coded using MedDRA and will be summarized in frequency tables by System Organ Class (SOC) and PT.

All medical history data will be included in a by-patient data listing.

7.3 Efficacy Analysis

The efficacy endpoints will be analyzed using the FAS.

7.3.1 Primary Efficacy Analysis

The primary endpoint of the study is the CR rate in patients with CIS, supported by duration of the CR.

A CR in patients with CIS is defined as at least one of the following:

- Negative cystoscopy and negative (including atypical) urine cytology
- Positive cystoscopy with biopsy-proven benign or low-grade NMIBC and negative cytology
- Negative cystoscopy with malignant urine cytology if cancer is found in the upper tract or prostatic urethra and random bladder biopsies are negative

The CR in patients with CIS for this endpoint must be documented on or after the Week 12 response assessment. Duration of CR in patients with CIS will be calculated from the documented onset of the CR to the assessment where the patient no longer meets the definition of CR. The durability of the CRs will be described using Kaplan-Meier plots of the duration of CR in responders. A tabular summary will also be created showing the proportion of patients with baseline CIS who are in response at 12, 24, 36, 48, 72 and 96 weeks using Kaplan-Meier estimates incorporating censoring (note that any patient who achieves response within 4 weeks of the planned assessment will be considered to be in response at that assessment, ie, a patient who has CR at 16 weeks will be a responder at 12 weeks). A similar tabular

This document is confidential.

summary will be created in the subset of patients with CIS who achieve a CR, that remain in response 12, 24, 36, 48, 52, 60, 72 and 84 weeks after the onset of response, for this summary, two methods will be used one which incorporates censoring and a second where patients who leave the study without losing response are considered failures. A by-patient swim lane plot of the time to CR and duration of CR in patients with CIS who respond will also be created. A similar summary will be created for the EFS (in all patients).

Sensitivity analyses for duration of response will be performed starting from the time the CIS lesion clears to time that new CIS lesions are identified, censoring patients with no CIS but other high-grade disease at the time of recurrence and a separate analysis looking at the time from response until any NMIBC is found (including low-grade disease).

A listing of CR rate and duration of response will be provided.

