## 9.6 Discontinuation of Therapy

Reasons for permanent discontinuation include the following:

1. In patients with CIS at baseline, failure to clear CIS lesions by Week 12; however, patients who clear CIS lesions but have low-grade disease should continue to be treated. Patients with CIS lesions that fail to clear may be followed by cystoscopy until they have a cystectomy or start an alternative treatment, but will be considered non-responders in the primary efficacy analysis
2. Recurrence of high-grade papillary lesions at the Week 12 cystoscopy or later or of CIS lesions after clearance. ***Only patients who meet the definition of recurrence should be discontinued. Patients with persistence or appearance of lower grade disease should not be discontinued***
3. Unacceptable toxicity, defined as a persistent Grade 3 AE or higher despite dosing delay (according to the AE management guidelines in Section 9.5)
4. Withdrawal of consent

Any patient without tumor in the bladder but presence of tumor in the upper urinary tract will not be classified as a failure in primary analyses and will continue study participation.

The reason for early discontinuation must be documented in the electronic case report form (eCRF). After discontinuation of study treatment for any reason, patients should be followed up for 30 days to assess safety.

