## 11. EFFICACY AND SAFETY ASSESSMENTS

### 11.1 Primary Efficacy Variable

The primary efficacy endpoint is, in patients with CIS at baseline, the:

- Proportion that achieves a CR at any time on or after week 12 and within the first 48 weeks

Complete response is defined as at least one of the following:

- Negative cystoscopy and negative (including atypical) urine cytology
- Positive cystoscopy with biopsy-proven benign or low-grade NMIBC and negative cytology
- Negative cystoscopy with malignant urine cytology if cancer is found in the upper tract or prostatic urethra and random bladder biopsies are negative

The complete response in patients with CIS for this endpoint must be documented on or after the Week 12 response assessment and on or prior to the Week 48 assessment. Duration of complete response in patients with CIS will be calculated from the documented onset of the complete response to the assessment where the patient no longer meets the definition of complete response. More generally, recurrence is defined as the reappearance or persistence of high-grade disease, or new high-grade disease. Recurrence must be biopsy proven. Persistence, appearance, or presence of lower grade disease will not be considered recurrence.

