**Maintenance Treatment Through Visit 23 (Week 48)**

Visit	V11	V12	V13	V14	V15	V16	V17	V18	V19	V20	V21	V22	V23
Week	12 Day 84	15	18	21	24	27	30	33	36	39	42	45	48
Mandatory response assessment for patients with CIS	X				X a				X a				X a
Urine sample for cytology (must be completed within 14 days prior to BC-819 administration)	X				X				X				X
Cystoscopy (must be completed within 14 days prior to BC-819 administration)	X				X				X				X
TUR/re-TUR/biopsy as clinically indicated	X				X				X				X
QOL assessment				X								X	
Administration of BC-819	X	X	X	X	X	X	X	X	X	X	X	X	X

aMandatory in patients who have not previously achieved a CR in their baseline CIS.

Detailed descriptions of procedures and timing are in Section 12.1.

Abbreviations: BC-819 = recombinant DNA plasmid complexed with polyethylenimine; CIS = carcinoma in situ; ECOG = Eastern Cooperative Oncology Group; QOL = quality of life; re-TUR = repeat transurethral resection; TUR = transurethral resection; V = visit.

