5.1 Efficacy Endpoints

5.1.1 Primary Efficacy Endpoint

The primary efficacy endpoint is, in patients with CIS at baseline, the:

- Proportion that achieves a CR at any time on or after week 12

Complete response is defined as at least one of the following:

- Negative cystoscopy and negative (including atypical) urine cytology
- Positive cystoscopy with biopsy-proven benign or low-grade NMIBC and negative cytology
- Negative cystoscopy with malignant urine cytology if cancer is found in the upper tract or prostatic urethra and random bladder biopsies are negative

The complete response in patients with CIS for this endpoint must be documented on or after the Week 12 response assessment. Duration of complete response in patients with CIS will be calculated from the documented onset of the complete response to the assessment where the patient no longer meets the definition of complete response. More generally, recurrence is defined as the reappearance or persistence of high-grade disease, or new high-grade disease. Recurrence must be biopsy proven. Persistence, appearance, or presence of lower grade disease will not be considered recurrence.

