7.1.3 Handling of Missing Data

Missing data handling rules for AE relationship to treatment and AE severity will be described in Section 7.4.1.

For efficacy endpoints, all efforts will be made to avoid missing data. If, however, it does occur, it will be handled as follows:

- If a visit has been missed and cytology cystoscopy results are available at the next visit and no disease is present, then the earlier visit will be counted as absence of disease.

This document is confidential.

- In addition, the count of absence of disease will be based on visit findings, meaning that if a patient missed a visit and at the next visit he/she experienced a recurrence, the recurrence will be counted only from the day on which evidence was provided.

Patients with CIS lesions that do not resolve by the 12-week cystoscopy will be classified as EFS events. For Kaplan-Meier analyses of EFS, they will be considered to have recurred at 1 day.

Any patient without tumor in the bladder but presence of tumor in the upper urinary tract will not be classified as failures in the CR and EFS analyses and will continue study participation.

Complete dates will be imputed from partial dates of adverse events and medications solely for the purpose of defining treatment emergence for adverse events and prior/concomitant status for medications. The imputed dates will not be presented in the listings. Dates will be defined using the hierarchy of derivations below.

Adverse events:

- For onset date:
 - If only the day part of the AE onset date is missing and occurs in the same month and year as the first dose date of study drug, the date of first dose of study drug will be used as the onset date of the AE. Otherwise, the first day of the month will be used to complete the onset date of the AE;
 - If the day and month parts of the AE onset date are missing and occur in the same year as the first dose of study drug, the date of the first dose of study drug will be used as the onset date of the AE. Otherwise, January 1st will be used to complete the onset date of the AE;
 - If the AE onset date is completely missing, the date of the first dose of study drug will be used as the onset date of the AE.
- For end date:
 - If only the day part of the AE end date is missing, the last day of the month will be used to complete the end date of the AE;
 - If the day and month parts of the AE end date are missing, December 31st will be used to complete the end date of the AE;

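### SAP 7.3.1 uses Kaplan-Meier for the share of all CIS patients in response at each week, but that share can rise and the curve cannot, so any first or regained CR after Week 16 is missed or counted too early

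*SAP*

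**What the plan says.** SAP 7.3.1 asks for a table of the proportion of patients with baseline CIS "who are in response at 12, 24, 36, 48, 72 and 96 weeks using Kaplan-Meier estimates", with censoring. Its one allowance for timing is that "any patient who achieves response within 4 weeks of the planned assessment will be considered to be in response at that assessment"; the SAP's own example is a CR at Week 16 counted at Week 12. The section does not say where the curve starts, what the event is, or how a patient not yet in response is coded.

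The endpoint leaves room for later responses. SAP 5.1.1 defines it as "Proportion that achieves a CR at any time on or after week 12". Protocol 11.1 adds an upper limit: "Proportion that achieves a CR at any time on or after week 12 and within the first 48 weeks". In Protocol Table 12.2, and again in SAP Table 2, the response assessments at Weeks 24, 36 and 48 are "Mandatory in patients who have not previously achieved a CR in their baseline CIS".

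Other passages point the other way. Protocol 9.6 lists as a reason for permanent discontinuation: "In patients with CIS at baseline, failure to clear CIS lesions by Week 12". It classes those patients as non-responders in the primary analysis even if they are followed by cystoscopy. The protocol synopsis and SAP 3.1 say much the same.

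A second table in SAP 7.3.1, and the duration plots, start at onset of CR and include responders only. Kaplan-Meier is appropriate there.

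**The concern.** Being in response is a state that patients enter and leave. At the first dose no CIS patient is in it; the share goes up as patients reach CR and down as they lose it. Kaplan-Meier estimates the probability that a single event has not yet happened. It begins at 100% and never increases, so it can describe leaving response but not entering it after the curve has begun to fall.

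A programmer given this text must choose a coding. If everyone not in CR at the Week 12 assessment is an immediate failure, a patient with a first CR at Week 24 never appears. If that patient is kept event-free until CR is lost, the patient is shown as responding at Week 12, before it happened. A patient who loses CR and regains it cannot be shown either.

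At stake is the SAP's table of durable response over all CIS patients, which supports the primary CR rate. Two programmers could produce different numbers from the same data, and neither set need equal the quantity named in the table.

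**Working it through.** **Plan's own figures.** No figure is stated for this table. The nearest are the power and interim statements for the CR rate. Taking as the success rule the smallest count whose Clopper-Pearson 95% lower limit exceeds 20%:
- n = 70 needs 22 responders; power at 40% is 94.5% (stated as over 95%).
- n = 100 needs 29; power at 35% is 91.5% (stated as about 92%).
- Interim: P(10 or more of 35 | 40%) = 94.2% and P(9 or fewer | 15%) = 97.1%, as stated.

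None of these uses the table in question.

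**Who could respond late.** The Week 12 rule concerns CIS lesions that have not cleared. CR also generally needs negative cytology. Take a patient at Week 12 with negative cystoscopy, malignant cytology, negative biopsies and no upper-tract or prostatic-urethral cancer. That patient is not in CR, yet has no biopsy-proven recurrence. Protocol 11.2 and SAP 5.1.2 say that repeated positive cystoscopy or cytology with negative biopsies is not an EFS failure. On these definitions the patient may continue and first reach CR later. The same finding at a later visit could end a CR that then returns.

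**Formulas, no censoring, N patients.**
- True share at week t: (entered CR by t − lost CR by t) / N.
- Coding A (not in CR at Week 12 = immediate failure): Week 12 responders still in CR at t / N. It is low by (late responders in CR at t) / N.
- Coding B (eventual responders event-free until loss): eventual responders who have not lost CR by t / N. It is high by (responders not yet in CR at t) / N.

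**Assumed numbers; the documents give no late-CR rate.** N = 70; 25 in CR at Week 12; about 20% of current responders lost every 12 weeks, in whole patients. The 25 become 20, 16, 13, 8 and 5 at Weeks 24, 36, 48, 72 and 96.

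| Percent in response | Wk 12 | Wk 24 | Wk 36 | Wk 48 | Wk 72 | Wk 96 |
|---|---|---|---|---|---|---|
| No late CR: true, A and B | 35.7 | 28.6 | 22.9 | 18.6 | 11.4 | 7.1 |
| 4 first CRs at Wk 24: true | 35.7 | 34.3 | 27.1 | 21.4 | 14.3 | 10.0 |
| 4 first CRs: coding B | 41.4 | 34.3 | 27.1 | 21.4 | 14.3 | 10.0 |
| 7 first CRs at Wk 24: true | 35.7 | 38.6 | 31.4 | 25.7 | 15.7 | 10.0 |
| 7 first CRs: coding B | 45.7 | 38.6 | 31.4 | 25.7 | 15.7 | 10.0 |

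Coding A gives the first row in every case.
- 4 late: 4/70 = 5.7 points low at Week 24 (A) or high at Week 12 (B).
- 7 late: 7/70 = 10.0 points low at Week 24 (A) or high at Week 12 (B).
- The error under A shrinks as late responders lose CR. At Week 96 it is 10.0 − 7.1 = 2.9 points in both cases.

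**Early leavers.** Suppose 7 of the 70 leave unassessed before Week 12 and are censored, and the non-responders fail at Week 12. The estimate is 25/63 = 39.7%. The CR rate over the full analysis set is 25/70 = 35.7%, so the table is 4.0 points higher.

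**The case against.** The strongest reply is that late responders may hardly exist. Patients whose CIS has not cleared by Week 12 are to be discontinued and classed as non-responders, so leaving out a later clearance follows the plan's own classification. The 4-week allowance carries a first CR up to Week 16 back to Week 12. The missed-visit rule in SAP 7.1.3 counts a missed visit as free of disease if the next visit shows none. If nobody enters or regains CR after Week 16 and nothing is censored, coding A equals the true share, as the first table row shows.

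All of that stands, and it bounds the point. A reader might infer that the table is bound to be wrong, or that no late response can be represented; the documents do not support either. Nor does the Week 12 rule settle the matter. It conflicts with the endpoint window and with the later mandatory assessments, and it does not cover patients with positive cytology and negative biopsies.

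Three other readings go too far:
- The rule that "they will be considered to have recurred at 1 day" is stated for Kaplan-Meier analyses of EFS. Nothing extends it to this table.
- The workshop benchmark at 18 to 24 months (Protocol 7.1.2) is for recurrence-free survival. EFS in CIS patients at Weeks 72 and 96 is the closer match, and SAP 7.3.2.1 gives it an exact binomial sensitivity analysis.
- Late responders are not lost from the report. They remain in the primary CR rate if classed as CR, and then in the duration analyses, swim-lane plot and listing.

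**Conclusion.** The table is wrong as written: the named estimator cannot give the named quantity for response patterns that the plan allows and schedules, and the origin, event and coding are undefined. The bias is about the share of CIS patients who first reach or regain CR after Week 16, less those who have since lost it. It is zero if there are none. It is 5.7 points for 4 of 70 and 10.0 points for 7 of 70, low at Week 24 or high at Week 12 depending on coding. These sizes rest wholly on assumed counts of late responders. The Week 12 excess from censoring early leavers is likewise an assumed example.

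The consequence is limited to a supportive durability table. The primary CR proportion, its confidence interval, the power and the interim rule do not change.

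**What to change.** Replace the estimator for this one table.

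1. At Weeks 12, 24, 36, 48, 72 and 96, report the number in CR divided by all full-analysis-set patients with baseline CIS, with a Clopper-Pearson 95% interval. Apply the 4-week allowance and the missed-visit rule in SAP 7.1.3 first, then count remaining missing or off-study patients as not in response.
2. If some patients have not reached a given week at the data cut, use an Aalen-Johansen estimate of the probability of being in response, with entry to, exit from and return to response as transitions.
3. Keep Kaplan-Meier for duration of CR from onset in responders.
4. Reconcile the passages that allow a later first CR (Protocol 11.1 and Table 12.2; SAP 5.1.1 and Table 2) with those on Week 12 discontinuation and non-responder status (protocol synopsis and 9.6; SAP 3.1), and state how each kind of patient enters the table.

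The cost is a paragraph of SAP text and one table shell. Rates may come out slightly lower than with censoring.

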7.3.2 Secondary Efficacy Analyses

The date of first dose, disease recurrence, disease progression, progression, death, last tumor assessment, last contact, EFS days, and PFS days will be reported in a by-patient listing.

7.3.2.1 Event-Free Survival and Time to Recurrence

EFS is defined as the time from first dose of study medication to the first recurrence of disease or death from any cause. Recurrence of disease is defined as

- Appearance of new high-grade disease (ie, new high-grade papillary disease or new CIS) or
- Failure to clear CIS lesions by Week 12 cystoscopy in patients with CIS at baseline

Recurrence must be biopsy proven. Persistence, appearance, or presence of lower grade disease will not be considered recurrence in the primary EFS analyses. Sensitivity analyses will be performed with lower-grade disease also considered an EFS event.

Any patient without tumor in the bladder but presence of urothelial carcinoma in the upper urinary tract or prostatic urethra will not be classified as failures in these analyses and will continue study participation.

Additionally, the overall proportion of patients who have high grade recurrence (and subcategories of persistent CIS, new CIS, new high-grade papillary disease), development of T2 or greater or metastatic disease, cystectomy and death will be summarized for the FAS, and the subgroups with CIS and papillary only disease.

Kaplan-Meier methods will be used to estimate the EFS (ie, percent surviving without a recurrence) and the 95% confidence interval at 12, 24, 36, 48, 72, and 96 weeks in all patients in the FAS and the subgroup of patients with CIS. The median EFS (ie, median time to recurrence) and its 95% confidence interval will also be estimated. Kaplan-Meier plots for EFS will be created.

A sensitivity analysis will also be performed to analyze EFS using binomial methods where patients are considered as being recurrence-free if they have documented recurrence-free survival by the specified time point. Only evaluable patients will be included in the analysis. Patients will be considered evaluable if they have enough follow-up to determine recurrence status at the time point being summarized or if they have discontinued treatment. Exact 95% confidence intervals for EFS will be calculated.

This document is confidential.

A sensitivity analysis for EFS will be performed where if a patient missed a visit and at the next visit he/she experienced a recurrence, the recurrence will be counted from the day of the missed assessment. An additional sensitivity analysis will be performed where recurrence of any NMIBC, including low-grade disease, is counted as an EFS event.

Time to recurrence is defined as first dose of study medication to the first recurrence of disease. Patients without a recurrence event (including death) will have their event time censored at the last recurrence-free disease assessment. All analyses performed for EFS, including all sensitivity analyses, will be performed for time to recurrence.

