#### **9.4.3 Maintenance Treatment**

Upon completion of the induction phase, patients will transition to a maintenance therapy schedule of BC-819 (ie, once every 3 weeks). The first maintenance treatment and visit will occur 12 weeks after enrollment (Visit 11). Treatments will continue every 3 weeks for 84 additional weeks until the end of the study (end of study [EOS] Visit 39) at 96 weeks.

Patients who have recurred with high-grade papillary carcinoma or with metastatic disease will be considered treatment failures and will be withdrawn from the study. All suspected recurrences (by direct visualization) must be documented by biopsy results.

Patients who are free of high-grade tumors or who are tumor-free (ie, patients benefiting from treatment) will be allowed to continue to receive maintenance therapy every 3 weeks per the schedule of treatment during the maintenance phase ([Table 12.2](#) and [Table 12.3](#)) as long as response status is maintained and they are not considered a treatment failure.

Patients will undergo repeat direct visualization (ie, cystoscopy  $\pm$  biopsy and cytology) and re-TUR (as needed for cause) every 12 weeks during the first and second year of the study.

All enrolled patients will complete the following quality of life questionnaires at the visits indicated in the study schedule ([Table 12.1](#) and [Table 12.2](#)):

- The European Organization for Research and Treatment of Cancer quality of life Questionnaire (EORTC QLQ-C30; a general questionnaire for cancer)
- Quality of Life Questionnaire–Non-Muscle-Invasive Bladder Cancer Questionnaire (QLQ-NMIBC24; a specific questionnaire for NMIBC disease)

The end of the study will be the 96-week visit (Visit 39) for all patients.

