7.3.2.2 Progression-Free Survival and Time to Progression

PFS is defined as the time from first dose of study medication to the first observation of disease progression or death. Progression is defined as the development of T2 or greater disease, which includes lymph node disease and distant metastasis.

Kaplan-Meier methods will be used to estimate the PFS (ie, percent surviving without a PFS event) and the 95% confidence interval at 48, 72, and 96 weeks in all patients in the FAS and the subgroup of patients with CIS. The median PFS and its 95% confidence interval will also be estimated. Kaplan-Meier plots for PFS will be created.

A sensitivity analysis of PFS will also be performed, which also includes an increase in stage from Ta or CIS to T1 as a progression event.

Time to progression is defined as first dose of study medication to the first observation of disease progression. Patients without a progression event (including death) will have their event time censored at the last progression-free disease assessment. All analyses performed for PFS, including all sensitivity analyses, will be performed for time to progression.

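### Protocol 9.4.3 makes metastatic recurrence a treatment failure, but the EFS, recurrence and CR-duration definitions do not name it, so metastasis with a clear bladder has no event there

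*SAP*

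**What the plan says.** **Failure rule.** Protocol 9.4.3 states: "Patients who have recurred with high-grade papillary carcinoma or with metastatic disease will be considered treatment failures and will be withdrawn from the study".

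**EFS and recurrence.** SAP 7.3.2.1 runs EFS from first dose to recurrence or death from any cause. Recurrence has two items. The first is "Appearance of new high-grade disease (ie, new high-grade papillary disease or new CIS", where the parenthesis closes. The second is failure to clear baseline CIS by the Week 12 cystoscopy. The section adds: "Recurrence must be biopsy proven". SAP 5.1.1 is wider: "recurrence is defined as the reappearance or persistence of high-grade disease, or new high-grade disease".

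**Time to recurrence.** The written censoring rule is: "Patients without a recurrence event (including death) will have their event time censored at the last recurrence-free disease assessment".

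**CR duration.** SAP 7.3.1 runs it from onset of CR "to the assessment where the patient no longer meets the definition of CR". That definition rests on cystoscopy, urine cytology and bladder biopsy. For responders who remain in response, the SAP plans two methods: one with censoring, and "a second where patients who leave the study without losing response are considered failures".

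**Progression.** SAP 7.3.2.2 states: "Progression is defined as the development of T2 or greater disease, which includes lymph node disease and distant metastasis".

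**Protocol endpoint text.** Protocol 11.2 and 13.5.3 define EFS as survival free of high-grade recurrence. Protocol 11.1 and 13.5.1 define recurrence through high-grade disease and end CR duration on the CR definition. The discontinuation list in Protocol 9.6 does not mention metastasis.

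**The concern.** A responder found to have nodal or distant metastasis while the bladder is clear must leave the study as a failure under Protocol 9.4.3. Yet none of the events written for EFS, time to recurrence or CR duration applies. The natural Kaplan-Meier handling is then to censor the patient. Leaving because of metastasis is informative, and censoring in place of an event can only raise the curve.

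These estimates matter. CR duration is the stated support for the primary endpoint (Protocol 13.5.1, SAP 7.3.1), and EFS at 48 weeks is the first secondary endpoint listed. The protocol also says a single-arm study of this kind can support a marketing application (Protocol 7.5).

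**Working it through.** **1. How each planned analysis treats the patient** (metastasis, clear bladder, withdrawn, alive at last contact)

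| Analysis | Source | Outcome as written |
|---|---|---|
| Kaplan-Meier EFS | SAP 7.3.2.1 | No event listed; censoring inferred, as no EFS censoring rule is written |
| Time to recurrence | SAP 7.3.2.1 | Censored under the written rule |
| CR duration, censoring method | SAP 7.3.1 | CR definition still met; censoring inferred |
| CR duration, second method | SAP 7.3.1 | Failure |
| Binomial EFS sensitivity analysis | SAP 7.3.2.1 | Evaluable because treatment stopped; not documented recurrence-free at later time points, so failure |
| PFS, time to progression | SAP 7.3.2.2 | Event |
| Summary of T2 or metastatic disease | SAP 7.3.2.1 | Counted, in its own category |

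Could the wider wording in SAP 5.1.1 bring metastasis into recurrence? It could be read so. But 7.3.2.1 restricts the phrase to papillary disease and CIS, and it tabulates metastatic disease apart from high-grade recurrence. The literal reading is the better one.

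**2. Size: inputs.** The plan gives no figure on this point, no rate of clear-bladder metastasis, and no scheduled follow-up imaging. All counts below are assumptions, except the planned total of 140 patients.

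Take one assessment with r at risk, d other events and m metastases. The Kaplan-Meier factor is (r − d)/r if the metastases are censored there and (r − d − m)/r if they are events. Later risk sets are the same, so censoring multiplies the later curve by (r − d)/(r − d − m), which is at least 1.

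**3. EFS at 48 weeks.** n = 140, with 70, 12, 10 and 8 events at Weeks 12, 24, 36 and 48. Metastases fall at Week 24, then 36, then 24.

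- One patient, censored: 70/140 × 58/70 × 47/57 × 39/47 = 28.3%. Counted: 39/140 = 27.9%.
- Two patients, censored: 70/140 × 58/70 × 47/57 × 38/46 = 28.2%. Counted: 38/140 = 27.1%.
- Three patients, censored: 70/140 × 58/70 × 46/56 × 37/45 = 28.0%. Counted: 37/140 = 26.4%.

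The gap is 0.5 to 1.6 points. The 95% half-width is about 1.96 × √(0.283 × 0.717/140) = 7.5 points. Starting from 56 or 84 Week 12 events gives the same range of gaps.

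**4. CR duration at 36 weeks after onset**

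- 22 responders (the fewest of 70 whose exact lower limit exceeds 20%), losses 4, 3, 3, one metastasis at 12 weeks. Censored: 18/22 × 14/17 × 11/14 = 52.9%. Counted: 11/22 = 50.0%. Gap 2.9 points; half-width 1.96 × √(0.50 × 0.50/22), about 21 points.
- 40 responders, losses 7, 5, 4, two metastases (12 and 24 weeks). Censored: 33/40 × 27/32 × 22/26 = 58.9%. Counted: 22/40 = 55.0%. Gap 3.9 points; half-width 1.96 × √(0.55 × 0.45/40), about 15 points.

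**5. Range.** A separate set of assumed counts places the censoring one assessment earlier. With 140 patients and 69 EFS events, one metastasis gives 50.5% censored against 50.0% counted, and three give 50.3% against 48.6%. With 28 responders and 14 losses, one gives 48.4% against 46.4%, and three give 46.4% against 39.3%. The last gap, 7.1 points, needs 3/28 = 10.7% of responders to have clear-bladder metastasis.

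**6. Does the second CR-duration method substitute?** Add three other leavers to the 22 responders (one at 12 weeks, two at 24). The main method gives 18/22 × 13/16 × 8/11 = 48.3%. Counting the metastasis gives 17/22 × 13/16 × 8/11 = 45.7%. Failing all leavers gives 8/22 = 36.4%. The second method captures the patient but does not isolate the effect.

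**7. What does not move.** The CR rate uses neither definition. Exact binomial checks give power of 94.5% for 70 patients (stated as over 95%) and 91.5% for 100 (stated as about 92%). The interim probabilities are 94.2% and 97.1%, as stated. None of these depends on this point.

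**The case against.** A reader might infer that the SAP dropped a failure criterion the protocol had set. The documents do not support that. The protocol's own EFS, recurrence, CR-duration and discontinuation text omits metastasis, and the SAP carries that text forward. The sentence in 9.4.3 is a treatment-plan rule on withdrawal. It is not a full failure definition, since it does not name CIS. The inconsistency begins inside the protocol.

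A reader might also infer that metastasis escapes the efficacy analyses. It does not. It is an event in PFS and time to progression, which are also Kaplan-Meier analyses, and it has its own planned summary for the full set and the CIS and papillary-only subgroups. The listing in SAP 7.3.2 shows recurrence and progression dates beside EFS and PFS days. A recorded death is an EFS event, although Protocol 9.6 provides only 30 days of safety follow-up after treatment stops.

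The best remaining defence is intent. CR and its duration are bladder endpoints, tumour in the upper tract or prostatic urethra is deliberately exempted, and spread is assigned to PFS. That is a fair reason to keep CR duration bladder-only. It is weaker for EFS, because 9.4.3 calls the patient a failure while the EFS curve would not. No success threshold or stopping rule uses either estimate, which lowers the priority.

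**Conclusion.** The point holds in a limited form. Read literally, metastasis with a clear bladder is no event in the Kaplan-Meier analyses of EFS and time to recurrence, and it does not end CR duration, although Protocol 9.4.3 treats it as failure. For EFS and CR duration, censoring is an inference from the absence of an event.

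The bias is favourable and probably small: 0.5 to 1.6 points on 48-week EFS and about 3 to 4 points on CR duration, with such patients assumed to be at most 5% of the group analysed. More frequent clear-bladder metastasis would enlarge it. It would be wrong to conclude that the primary CR result, the power or the futility rule is affected. This is a change to consider, not a condition for a valid analysis.

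**What to change.** - **SAP 7.3.2.1:** add progression as defined in 7.3.2.2 (T2 or greater, lymph node disease or distant metastasis) as an EFS and recurrence event, dated at first documentation. Do not apply the biopsy requirement to metastasis. Keep the exemption for upper-tract and prostatic-urethra tumour.
- **SAP 7.3.1:** let the same event end CR duration. If the sponsor prefers a bladder-only duration, add this version as a sensitivity analysis.
- **SAP 7.7:** record the change, since that section now declares none.
- **Protocol:** align the EFS wording with 9.4.3.
- In the same edit, it would help to write the censoring rule for EFS and CR duration, as only time to recurrence has one.

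The cost is a few lines in the SAP, a declared change and a protocol wording alignment, possibly by amendment. No visits, procedures or patients are added. The EFS, time-to-recurrence and CR-duration estimates may come out slightly lower.
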